4. CHANGES IN THE PLANNED ANALYSIS OF THE STUDY

For the further endpoint of change from screening Visit 1a in PRECIS individual items and domain scores at Week 24, only the PRECIS domain scores will be analyzed, and the PRECIS individual items will not be analyzed.

Definition of baseline for the assessments of efficacy, PANSS and C-SSRS will include assessments up to but no later than the day of the first administration of study medication.

5. ENDPOINTS(S)

5.1 PRIMARY ENDPOINT(S)

The primary endpoint is

- Change from baseline in MCCB overall composite T-score at Week 26.

MCCB assessments are planned to be performed at screening (Visit 1), baseline (Visit 2), Week 12 (Visit 6), and Week 26 (Visit 11/EOT) or any early end of treatment visit.

Any post-baseline MCCB assessments performed within 28 days of the previous assessment will be considered invalid because of potential practice effects and will be excluded prior to any subsequent data handling and therefore from the planned analyses (5).

The MCCB overall composite T-score will be derived from seven domain scores from a total of ten tests (see CTP Table 5.1: 1). A larger MCCB overall composite T-score indicates better cognition.

5.2 SECONDARY ENDPOINT(S)

5.2.1 Key secondary endpoint(s)

The key secondary endpoints are:

- Change from baseline in Schizophrenia Cognitive Rating Scale (SCoRS) interviewer total score at Week 26
- Change from baseline in Virtual Reality Functional Capacity Assessment Tool (VRFCAT) adjusted total time T-score at Week 26.

A lower rating in SCoRS reflects a lesser degree of impairment. A higher T-score in VRFCAT indicates a better functional outcome.

The endpoints will be used as defined in CTP Section 5.

[figure not shown]
5.2.2 Secondary endpoint(s)

[figure not shown]
The other secondary endpoints are:

[figure not shown]
- Change from baseline in the T-score of the number of correct responses on Tower of London (ToL) at Week 26
- Change from screening Visit 1a in Patient Reported Experience of Cognitive Impairment in Schizophrenia (PRECIS) total score at Week 24

[figure not shown]
A higher T-score in ToL indicates a better outcome. A lower score in PRECIS corresponds to a better patient experience.

The endpoints will be used as defined in CTP Section 5.

6. GENERAL ANALYSIS DEFINITIONS

6.1 TREATMENT(S)

For basic study information on treatments to be administered, assignment of treatment groups, select of doses, see CTP Section 4.

Table 6.1: 1 lists the two treatment groups in this study. Table 6.1: 2 defines the analysing treatment period for safety analyses. For this study, the residual effect period (REP) is defined as 12 days after the last dose of trial medication.

Table 6.1: 1 Treatment descriptions

Long Name	Short Name
Placebo	Placebo
Iclepertin 10 mg QD	Iclepertin 10 mg

Table 6.1: 2 Analysing treatment periods (same for all treatment groups)

Analysing Treatment Period	Start Date	End Date
Screening period	Date of informed consent	Date of the first treatment administration – 1 day
On-treatment period	Date of the first treatment administration	Date of the last treatment administration + REP
Post-treatment period	Date of the last treatment administration + REP + 1 day	Date of the last per protocol visit

REP is the residual effect period which is defined as 12 days after the last dose of trial treatment.

6.2 IMPORTANT PROTOCOL DEVIATIONS

Handling of iPDS in analyses is described in the iPDS specification document and stored in the Trial Master File (TMF) in the electronic Document Management System (eDMS).

6.3 INTERCURRENT EVENTS

Definition and technical specification of protocol defined intercurrent events (ICEs) are listed in [Table 6.3: 1](#). In general, when handled under the hypothetical approach, data collected during the off-treatment period of an ICE will be considered irrelevant to the estimand and excluded from the analysis. While off-treatment data will be excluded, the patient will still be considered as on-treatment (hypothetically) from an analysis perspective by the statistical models, and during any imputations.

For an ICE of temporary treatment discontinuation or interruptions, the off-treatment period spans from the last treatment administration prior to the interruption + REP to the restart of

the study medication. For an ICE of early permanent treatment discontinuation, the off-treatment period starts from the last treatment administration + REP. [Figure 6.3: 1](#) illustrates the on-/off-treatment status after each type of ICEs. When there is more than one ICE of early permanent treatment discontinuation, any treatment policy ICE take precedence in data and analysis handling over any hypothetical ICE.

ICEs of change in concomitant therapies and other ICEs will always be considered as part of the treatment policy in the primary and all supplementary estimands. ICEs of this category will not affect the on-/off-treatment status which is only determined by changes in the study medication. These ICEs will be listed and summarized descriptively but will not be explicitly accounted for in the inferential analysis of efficacy.

Table 6.3: 1 Definition and technical specification of intercurrent events

Type of Intercurrent Event	Definition and Documentary Sources	Handling under the Primary Estimand
Temporary Treatment Discontinuations or Interruptions		
Exacerbation or acute episode of schizophrenia resulting in interruption of treatment	
Identified from data collected in the Temporary Trial Treatment Discontinuation and Adverse Event pages of the CRF:
 
 - Temporary discontinuation of trial treatment reported with reason being “Adverse Event”, and - AE category reported as “Schizophrenia Relapse” or MedDRA preferred term coded as “Schizophrenia” 	Treatment policy
Temporary treatment discontinuation or interruption due to other reasons	Identified from data collected in the Temporary Discontinuation page of the CRF.	Hypothetical – only data collected from the end of REP after the interruption, to end of the interruption will be subject to exclusion from the analysis
Temporary treatment-switch due to dispensation error	Identified from the dispensation records. Temporary treatment-switch will be handled as temporary interruptions in the same way for both directions (iclepertin to placebo or placebo to iclepertin)	Hypothetical – only data collected from the end of REP after the treatment switch, to end of the treatment switch will be subject to exclusion from the analysis
Early Permanent Treatment Discontinuation		

Exacerbation or acute episode of schizophrenia resulting in early termination of treatment	Identified from data collected in the Adverse Event page of the CRF: 
 - “Drug Withdrawn” reported in the Action Taken with Study Treatment field, and - Category reported as “Schizophrenia Relapse” or MedDRA preferred term coded as “Schizophrenia” 	Treatment policy
Investigator assessed drug-related adverse events which lead to early termination of study medication	Identified from data collected in the Adverse Event page of the CRF: 
 - “Drug Withdrawn” reported in the Action Taken with Study Treatment field, and - “Yes” reported in the Relationship to Study Treatment field 	Treatment policy
Protocol-defined drug withdrawal due to treatment – haemoglobin decrease	Identified from data collected in the End of Treatment and Adverse Event pages of the CRF and laboratory data: 
 - Subject who did not complete the planned treatment period as reported in the End of Treatment page with reason being “Adverse Event”, and - AE indicating haemoglobin decrease with action taken being “Drug Withdrawn” 	Treatment policy
Protocol-defined drug withdrawal due to treatment – CYP3A4 inhibitors or CYP3A4 sensitive drugs with NTI	Identified from data collected in the End of Treatment page of the CRF: 
 - Subject who did not complete the planned treatment period as reported in the End of Treatment page with “Protocol Deviation” as the reason, and - Use of CYP3A4 inhibitors or CYP3A4 sensitive drugs with NTI specified as the detailed reason of discontinuation 	Treatment policy
Early termination of study	Identified from data collected in the End of Treatment page of the CRF:	Hypothetical

[figure not shown]
medication due to other AEs	
 - Subject who did not complete the planned treatment period as reported in the End of Treatment page with reason being “Adverse Event” and not otherwise covered by any of the ICEs above. 	
Early termination of study medication due to perceived lack of efficacy	
Identified from data collected in the End of Treatment page of the CRF:
 
 - Subject who did not complete the planned treatment period as reported in the End of Treatment page with reason being “Perceived Lack of Efficacy”. 	Hypothetical
Early termination of study medication due to other reasons	
Identified from data collected in the End of Treatment page of the CRF:
 
 - Subject who did not complete the planned treatment period as reported in the End of Treatment page for reasons not covered by any of the ICEs above. 	Hypothetical

Change in Concomitant Therapies and Other ICEs

Change in background medication	
Identified from data collected in the Concomitant Medications page of the CRF:
 
 - Start of a new or stop of an on-going antipsychotic, benzodiazepines (or derivatives), anticholinergics, antiepileptics, or antidepressants during the on-treatment period, or - Change of dosage or dosing frequencies of an on-going antipsychotic, benzodiazepines (or derivatives), anticholinergics, antiepileptics, or antidepressants during the on-treatment period 
See Table 10.7: 1 for definitions of antipsychotics, benzodiazepines (or derivatives), anticholinergics, antiepileptics, and antidepressants.
	Treatment policy
Change in psychotherapy	Identified from data collected in the Psychotherapy page of the CRF:	Treatment policy

	
 - Change in frequency, setting or session of a psychotherapy during the on-treatment period 	
Change in other non-pharmacological therapy	
Identified from data collected in the Concomitant Non-Drug Therapies page of the CRF:
 
 - Start of a new non-drug therapy or stop of an on-going non-drug therapy during the on-treatment period 	Treatment policy
Change in study partner in the assessment of functional capacity, e.g. SCoRS	
Identified from data collected in the Study Partner Informed Consent page of the CRF and date/time of SCoRS assessments:
 
 - Any new study partner informed consent signed between the baseline SCoRS assessment and the SCoRS assessment being considered 	Treatment policy – relevant only to endpoints from the SCoRS assessment

Figure 6.3: 1 On-/off-treatment status of the study medication for efficacy analysis after ICEs

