## 2. TRIAL OBJECTIVES AND ENDPOINTS

### 2.1 MAIN OBJECTIVES, PRIMARY AND SECONDARY ENDPOINTS

#### 2.1.1 Main objectives

The primary objective of this phase III pivotal trial in CIAS is to assess the efficacy in improving cognitive impairment using MCCB in patients with schizophrenia treated for 26 weeks with Icleperitin 10mg as compared with placebo.

The key secondary objective is to assess the efficacy in daily functioning of 26-week treatment with Icleperitin 10mg as compared with placebo in terms of Schizophrenia Cognition Rating Scale (SCoRS) and Virtual Reality Functional Capacity Assessment Tool (VRFCAT).

The secondary objectives are to assess the efficacy in improving reasoning and problem solving and patients' experience of cognitive impairment associated with their disease.

Patients will be required to be on stable antipsychotic treatment at the time of inclusion.

The primary treatment effect of interest is defined in the primary estimand framework as specified in detail in [Section 7](#). All efforts will be taken to continue to collect efficacy data at planned visits after patients discontinued trial treatment following an intercurrent event. For patients who discontinued trial treatment after intercurrent events that will be handled by the treatment policy approach, these observed off-treatment data will be included in the primary analysis. For patients who discontinued trial treatment after other intercurrent events that will not be handled by the treatment policy approach, these observed off-treatment data will be censored and excluded from the primary analysis.

In summary, the primary treatment effect of interest is the effect obtained at the primary time point if patients had stayed on the treatment, i.e. taking the trial medication for the full treatment duration while allowing the following intercurrent events: change in concomitant medications or background non-pharmacological therapy, change in study partner, and treatment interruption or discontinuation due to exacerbation, an acute episode, adverse events (AEs) that are considered drug related and protocol-defined drug withdrawal.

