## **7. STATISTICAL METHODS AND DETERMINATION OF SAMPLE SIZE**

The primary efficacy objective is to assess the absolute difference in adjusted mean change from baseline to Week 26 in MCCB overall composite T-score (cognition) for once daily oral treatment with Iclepertin 10mg QD as compared with placebo in patients with CIAS. The key secondary efficacy objectives are to assess the absolute difference in adjusted mean change from baseline to Week 26 in SCoRS interviewer total score and adjusted total time T-score in VRFCAT between Iclepertin 10mg QD and placebo. Intercurrent events will be addressed using a strategy that differs depending upon the nature of the intercurrent event.

The treatment effect for the following treatment policy is of interest: patients remain on randomized treatment for the duration of the trial unless an exacerbation or acute episode or an event considered to be drug-related interrupts or discontinues treatment. Changes in background medication or non-pharmacological intervention are allowed.

Estimation will assume that the policy is followed by all randomized patients. All measurements obtained for patients while on this policy are therefore relevant for the estimation of the primary estimand, while measurements obtained after a deviation from this policy are not relevant for the estimation of the primary estimand.

The following intercurrent events are considered to form part of the treatment policy being assessed and hence subsequent measurements are included in the primary analysis of the endpoint:

- Change in background medication (e.g. antipsychotics, etc)
- Change in non-pharmacological therapy (e.g. cognitive therapy, any kind of psychotherapy, nicotine withdrawal therapy, diet, etc)
- Exacerbation or acute episode which results in interruption or early termination of treatment
- Investigator assessed drug-related adverse events which lead to early termination of study medication
- Protocol-defined drug withdrawal due to treatment, e.g. haemoglobin decrease, concomitant medications with CYP3A4 substrates
- Change in study partner in the assessment of functional capacity, e.g. SCoRS

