All other intercurrent events are considered to represent breaks from the treatment policy and therefore confound estimation of the treatment effect of interest. Such intercurrent events would include, for example, early termination of treatment due to reasons unrelated to treatment (e.g. consent withdrawal, incarceration, somatic illness like stroke, cardiovascular events, etc, hospitalization due to somatic illness). Measurements after these intercurrent events are excluded from the primary analyses.

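### SAP Table 6.3:1 treats pauses for drug-related adverse events as hypothetical, although the protocol's estimand statements place them inside the treatment policy

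*SAP*

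**What the plan says.** Protocol Section 7 defines the policy of interest as staying on randomized treatment "unless an exacerbation or acute episode or an event considered to be drug-related interrupts or discontinues treatment". It continues: "All measurements obtained for patients while on this policy are therefore relevant for the estimation of the primary estimand". The synopsis and Section 2.1.1 use matching wording and list, among the allowed events, "treatment interruption or discontinuation due to exacerbation, an acute episode, adverse events (AEs) that are considered drug related and protocol-defined drug withdrawal".

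The bullet list in Section 7 then names the events that form part of the policy. For schizophrenia it reads "Exacerbation or acute episode which results in interruption or early termination of treatment". For drug-related events it reads "Investigator assessed drug-related adverse events which lead to early termination of study medication", with no mention of interruption. The next paragraph adds: "All other intercurrent events are considered to represent breaks from the treatment policy".

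SAP Table 6.3:1 has one treatment-policy row for interruptions, limited to exacerbation or acute episode of schizophrenia. A drug-related adverse event appears only where it leads to early termination, also under treatment policy. Apart from dispensing errors, every other pause goes to "Temporary treatment discontinuation or interruption due to other reasons". That row is hypothetical and excludes data from the end of the residual effect period until the pause ends. SAP Section 6.7 keeps such off-treatment data out of the visit mapping. SAP Section 4 lists two changes (PRECIS individual items and the definition of baseline) and does not mention this one.

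**The concern.** The primary estimand needs one rule for which measurements count. A reader of the synopsis, Section 2.1.1 or the Section 7 policy sentence expects measurements taken during a drug-related pause to be in the primary analysis. The SAP takes out those more than 12 days after the last dose.

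The result is also hard to defend on substance. If a drug-related event ends treatment, the off-drug values stay in. If the same event causes a pause, the off-drug values are dropped. Protocol Sections 3.3.4.1 and 6.2.5.1 allow patients who stopped to restart, so one patient can pass from one class to the other. The precedence rule in SAP Section 6.3 covers only several permanent discontinuations.

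The same strategy governs SCoRS, VRFCAT, Tower of London and PRECIS (SAP Sections 7.5.1.1 and 7.5.2). What is at stake is the definition of the estimand. The size of the estimate is hardly affected.

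**Working it through.** **1. The texts side by side**

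| Place | Drug-related event, pause | Drug-related event, permanent stop |
|---|---|---|
| Protocol synopsis and 2.1.1 | inside the policy | inside the policy |
| Protocol 7, policy sentence | inside the policy | inside the policy |
| Protocol 7, bullet list | not named | inside the policy |
| SAP Table 6.3:1 | other reasons: hypothetical | treatment policy |

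The columns agree in the first two rows and part in the last two.

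**2. Which values can be lost**

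The residual effect period is 12 days (SAP 6.1). A value planned for day D is lost if the last dose was on or before D − 12 and treatment had not restarted by the assessment. The limit is one day earlier if the day of last dose plus 12 still counts as on treatment, as in SAP Table 6.1:2.

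- MCCB, SCoRS and VRFCAT at Week 12: 85 − 12 = Day 73 (or 72). The analysis window is Day 2 to 126, so an assessment after restart within it still counts.
- PRECIS at Week 24, the endpoint value: 169 − 12 = Day 157 (or 156).
- Week 26 values: lost only if the pause is still open at the assessment. A pause that never ends and is recorded as drug withdrawn with a related event goes to the termination row, and its data are kept.

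Protocol 3.3.4.1 asks that the sponsor be informed of interruptions longer than 10 days, so pauses of about this length are foreseen.

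**3. The plan's own figure, for scale**

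With 220 per arm, effect size 0.35 and one-sided 0.025, the noncentrality is 0.35 × √(220/2) = 3.67. Power is Φ(3.67 − 1.96) ≈ 95.6%, which matches the stated 95% and the 95.6% in Table 7.5:1. Also 220/0.75 = 293.3, stated as 293 per arm. The effect of 2 points with SD 5.8 gives 2/5.8 = 0.345.

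**4. Size for MCCB at Week 26**

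Assumptions, none of them in the documents: 3 or 9 of 293 active patients (1% or 3%) are paused at the Week 12 test; they lose the full 2 points at Week 12 and nothing at Week 26; the correlation ρ between visits is 0.5 or 0.7; 25% of Week 26 values are missing at random. The SD is 5.8 at both visits, so the regression slope equals ρ.

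A lost Week 12 value reaches the Week 26 contrast only through the repeated-measures model. The mean shift, SAP rule minus keeping all data, is about −ρ × 2 × (q − p). Here p is the share paused in the arm and q the share paused among those with a Week 26 value.

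If every paused patient has Week 26:

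- 9 paused: q = 9/(0.75 × 284 + 9) = 9/222 = 0.0405; p = 9/293 = 0.0307; shift −0.010 (ρ = 0.5) or −0.014 (ρ = 0.7).
- 3 paused: q = 3/(0.75 × 290 + 3) = 3/220.5 = 0.0136; p = 3/293 = 0.0102; shift −0.003 or −0.005.

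If paused patients share the 25% missingness, then q = p on average and the mean shift is zero.

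A simulation of a two-visit likelihood model without covariates (293 per arm, 1,500 runs per setting) agrees with this. Mean shifts were −0.003 to −0.014 in the first case and within 0.0005 of zero in the second. The 95th percentile of the absolute shift in a single trial was 0.012 to 0.049 points. The SD of the estimate was 0.51 to 0.54, so 0.049 is about a tenth of a standard error.

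**5. PRECIS**

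Table 7.5:1 assumes an effect size of 0.2 or 0.275. If 1% to 3% of the active arm had lost all of 0.275 at Week 24, keeping their values would lower the mean difference by 0.01 × 0.275 = 0.003 to 0.03 × 0.275 = 0.008 SD. The standard error with 220 per arm is √(2/220) = 0.095 SD.

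**The case against.** The strongest reply is that the SAP follows the operative list. Its row for drug-related events matches the Section 7 bullet, SAP Section 3 says the plan is based on Section 7, and Section 2.1.1 is a summary that defers to Section 7 for detail. That stands in part: the SAP does not contradict every part of the protocol. But the policy sentence, and the statement that data on the policy are relevant, are themselves in Section 7 and agree with both summaries.

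It can also be said that the numerical effect is negligible, that permanent drug-related stops are already covered, and that the planned supplementary analysis with treatment policy for all events (Protocol 7.2.2) keeps these values. The first two stand. The third does not settle the matter, because that analysis applies treatment policy to every event and so targets a different estimand. SAP Figure 6.3:1 was not visible, but it is described as showing on- and off-treatment status; the handling strategy is set in the table.

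A reader might go further and infer a third competing rule from "Measurements after these intercurrent events are excluded from the primary analyses", which has no end point: that a drug-related pause removes everything afterwards, including values after restart. The documents do not support this. The synopsis and Section 2.1.1 limit censoring to observed off-treatment data, the examples in that paragraph are mainly early terminations, and the SAP window ends at restart.

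**Conclusion.** The inconsistency is real. The protocol's estimand statements place interruptions for drug-related events inside the treatment policy, and the SAP's primary-analysis rule excludes part of the resulting data without declaring a change.

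It is minor in size. Only pauses longer than 12 days that span an assessment matter: mainly the Week 12 value for MCCB, SCoRS and VRFCAT, and possibly the Week 24 value for PRECIS. Under the assumed 1% to 3% paused at the test, the MCCB contrast moves by at most about 0.014 points on average. The documents give no interruption rate, so every magnitude here is conditional. The calculation also places pauses in the active arm only and omits the baseline and stratum terms.

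A reader might infer that the SAP rule favours the active arm. That does not follow: the sign depends on the assumed loss at Week 12 and on who returns at Week 26, and no direction is claimed. The reason to act is that the primary estimand should have one rule, fixed before unblinding.

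**What to change.** Before unblinding, in the SAP:

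1. Add a treatment-policy row to Table 6.3:1 for investigator-assessed drug-related adverse events resulting in interruption. Identify it from the Temporary Discontinuation and Adverse Event pages and the Relationship to Study Treatment field.
2. Limit the row for other reasons to the remaining pauses.
3. Record the change in SAP Section 4.

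At the next protocol amendment, extend the Section 7 bullet for drug-related events to cover interruption as well as early termination, as the exacerbation bullet already does. As a wording clarification only, state there that the measurements excluded after other intercurrent events are off-treatment measurements.

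The cost is one new table row, one narrower row and one Section 4 entry, with the protocol wording waiting for an amendment needed anyway. Table 6.3:1 already uses these CRF pages and fields. The downside is that a few off-drug values stay in the primary analysis, as the stated estimand implies.

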### **1.2.2 Residual Effect Period**

The Residual Effect Period (REP) of Iclepertin is defined as 12 days after the last dose of trial medication. This is the period after the last dose with measurable drug levels and/or pharmacodynamic effects still likely to be present.

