#### 1.2.4 Clinical Pharmacology

Iclepertin has a half-life ranging from 37 to 59 h. Steady state is reached after 6 days of dosing with accumulation ratios for Cmax ranging from 1.96 to 2.63 and for AUC from 2.31 to 3.21. In the single rising dose study 1346.1 ([c02820512](#)) at 25 mg dose the effect of a high calorie, high fat meal resulted in an increased exposure with fed/faasted ratio for Cmax 142% and for AUC0-tz 126%. The multiple rising dose study 1346.2 ([c03572014](#)) looked at the effect of a light meal, and the effect is much less pronounced. In phase II, patients were allowed to take Iclepertin "with or without" food as no clinically relevant effect on exposure was expected. In Phase III 10mg Iclepertin will also be administered with or without food as the expected increase of exposure is below the exposure already observed in previous trials, e.g. 1346-0009 ([c31477880](#)).

As the mechanism of action involves enhancement of brain plasticity (which is higher during day than during night), dosing should occur after waking up (i.e. preferably in the morning). Pharmacokinetic parameters between young and elderly healthy subjects, and between Japanese, Chinese and Caucasian subjects are comparable.

Iclepertin crosses blood-brain barrier and the required 50% glycine increase in the CSF was observed after multiple dosing of 10 mg Iclepertin.

Iclepertin is a sensitive substrate of CYP3A4, and co-administration of moderate to strong CYP3A4 inducers / inhibitors is not permitted, as this reduces / increases plasma concentrations of Iclepertin. CYP3A4 sensitive drugs with narrow therapeutic index (NTI) are restricted during the treatment period. For CYP3A4 sensitive drugs without NTI investigators should assess if dose adjustments and/or monitoring of the underlying disease is clinically required for patients who are taking such drugs. List of prohibited medication is inserted in the ISF, although the impact on common comedication in this target population is minimal. Details can be found in Investigator Brochure that is updated and provided to sites at regular intervals.

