#### **4.1.4 Drug assignment and administration of doses for each patient**

Dispensing of medication kits for the double-blind treatment period will begin at Visit 2. Throughout the treatment period, 2 trial medication kits will be provided at each visit. Medication assignment will be provided through IRT. The assigned medication kit numbers must be entered in the eCRF, and the corresponding medication kits must be given to the patient. The duration of treatment is 26 weeks. At each of the visits, patients will receive supplies for a total of 4 weeks (21 treatment days plus 7 days reserve).

The first dose of study medication will be taken at the end of Visit 2 under supervision of the investigator or delegated site staff, after all Visit 2 assessments have been completed. In case the Visit 2 is split into 2 sequential days, the first dose of study medication should be taken on the second day of split the visit, after all Visit 2 assessments have been completed.

Throughout the study, patients should be instructed to take 1 tablet orally with water and with or without food after waking up. If a dose is missed by more than 12 hours, that dose should be skipped and the next dose should be taken as scheduled.

Patients should be instructed **not** to take their trial medication AT HOME on each visit day as patients will be dosed at the site. Dosing should occur approximately 24 hours after the drug administration of the preceding day.

The last dose of study medication should be taken on the day before the EoT Visit. In case the EoT Visit is split into 2 sequential days, the last dose of study medication should be taken on the day before the first day of the split visit.

On longer visit days the dosing may occur in the afternoon.

A dose reduction of Iclepertin is not possible.

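### The dispensing-error rule in SAP Table 6.3: 1 applies the 12-day residual period alike in both directions, so some values that placebo patients give on iclepertin stay in the placebo arm (minor)

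*SAP*

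**What the plan says.** Protocol Section 7 does not name dispensing errors among its intercurrent events, so the SAP row governs. In SAP Section 6.3, Table 6.3: 1, the row reads: "Temporary treatment-switch will be handled as temporary interruptions in the same way for both directions", and it names both iclepertin to placebo and placebo to iclepertin. The handling column is hypothetical and limits the excluded data: "only data collected from the end of REP after the treatment switch, to end of the treatment switch will be subject to exclusion".

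The general text of SAP Section 6.3 gives the parent rule for temporary interruptions: "the off-treatment period spans from the last treatment administration prior to the interruption + REP to the restart of" study medication. SAP Section 6.1 sets the length: "the residual effect period (REP) is defined as 12 days after the last dose of trial medication". Protocol Section 1.2.2 gives its meaning: "This is the period after the last dose with measurable drug levels and/or pharmacodynamic effects still likely to be present".

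SAP Section 6.4 analyses efficacy by randomised arm. SAP Section 6.7 removes off-treatment values from visit mapping unless the event is handled by treatment policy. A value that the switch rule does not exclude is therefore an ordinary value of the randomised arm.

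**The concern.** REP is a property of iclepertin. When an iclepertin patient is given placebo by mistake, drug and effect persist for a while, so it is reasonable to wait 12 days before treating the patient as off treatment. A placebo patient given iclepertin has no earlier drug effect to wait out. Exposure starts with the first wrong dose and, by the plan's own definition, lasts until 12 days after the last one. The common rule leaves both ends of that exposure in the data: the opening days on active drug, and the residual period after the switch ends.

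At stake is whether a placebo value in the hypothetical analysis means what it should, namely the score the patient would have had on placebo throughout. If a contaminated MCCB, SCoRS or VRFCAT value enters at Week 26, it pulls the placebo mean toward the iclepertin mean.

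The SAP uses the opposite logic elsewhere. The note under Table 6.7: 9 drops placebo patients' ophthalmological assessments once iclepertin has been given in the extension trial, with no waiting period. That is a safety analysis, but the reasoning carries over.

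**Working it through.** **Inputs.** REP is 12 days (SAP 6.1). Half-life is 37 to 59 h (Protocol 1.2.4). Each dispensing visit supplies 21 treatment days plus 7 in reserve (Protocol 4.1.4). Visit 10 is on Day 169 ± 3 and EoT on Day 183 ± 3 (Protocol Flow Chart). Sample size uses 220 evaluable patients per arm, a standardized effect of 0.35, a 2-point difference and an SD of 5.8 (Protocol 7.5).

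**Days kept for a placebo patient given iclepertin.** Call the first wrong dose day 1 and the length of the switch L days. The last correct dose is on day 0, so REP ends on day 12. The rule excludes max(0, L − 12) days. Days on drug or within REP of it number L + 12.

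| L | Exposed days | Excluded | Kept as placebo |
|---|---|---|---|
| 7 | 19 | 0 | 19 |
| 12 | 24 | 0 | 24 |
| 14 | 26 | 2 | 24 |
| 21 | 33 | 9 | 24 |
| 28 | 40 | 16 | 24 |

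For one 21-day interval, days 1–12 are kept, 13–21 excluded and 22–33 kept: 24/33 = 73%. Counting REP from the first wrong dose instead, or excluding the boundary day itself, moves this by one day (25 or 23 of 33).

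**Exposure in the kept days.** Protocol 1.2.4 states "Steady state is reached after 6 days of dosing". From the half-life, the fraction of steady state reached is 1 − 0.5^(t/half-life): 82% to 93% at day 6 and 97% to 99.5% at day 12. After the last dose, the level falls to 0.5%–3.4% only at day 12.

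**Routes to the Week 26 analysis.**

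- *Wrong kit at Visit 10, short gap to EoT.* The gap is 14 + d days, where d is the difference between the two visits' deviations and runs from −6 to 6. Of the 49 day pairs, 7 − |d| have difference d. If REP is counted from the switch day, gaps of 12 days or less are kept: 1+2+3+4+5 = 15. Counted from the last correct dose, as the general text of Section 6.3 does, gaps of 11 or less are kept: 1+2+3+4 = 10. If the boundary day is also excluded, gaps of 10 or less are kept: 1+2+3 = 6. These counts assume that the excluded interval is still open on the test day, and they weight all pairs equally.
- *Wrong kit at Visit 9, corrected at Visit 10.* At nominal visits the last wrong dose is on Day 168, and 168 + 12 = Day 180, the first allowed EoT day. A Day 180 test lies within REP and nothing excludes it.
- *Early-termination test.* SAP Table 6.7: 1 maps Days 2–126 to Week 12 and Day 127 onward to Week 26, so an early end-of-treatment test soon after a wrong kit can enter either visit.

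**Size.** The plan's power reproduces: Φ(0.35 × √(220/2) − 1.96) = Φ(1.711) = 95.6%, against 95% in Protocol 7.5 and 95.6% in its Table 7.5: 1. One contaminated patient moves the placebo mean by at most 2/220 = 0.009 points. The standard error of the difference is about 5.8 × √(2/220) = 0.55, so this is about 1.6% of one standard error. The documents give no error rate. As an assumed range, if a fraction f of placebo Week 26 values carried the full drug effect, the standardized effect would be 0.35 × (1 − f):

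| f | Effect | Power |
|---|---|---|
| 0.5% | 0.348 | 95.5% |
| 1% | 0.347 | 95.3% |
| 2% | 0.343 | 94.9% |
| 5% | 0.333 | 93.7% |

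**The case against.** A reader might infer that even on nominal dates a Week 26 test after a wrong kit at Visit 10 is kept. The Protocol says "The last dose of study medication should be taken on the day before the EoT Visit", so the last wrong dose is on Day 182 and the Day 183 test would come after the switch. The documents do not support this firmly. The SAP does not say whether a switch ends with the last wrong dose or with the first correct one. Switches are handled as interruptions, whose off-treatment period runs to the restart of medication. After a Visit 10 error there is no restart, because no dose is given at EoT (Flow Chart, footnote 5). On that reading the interval is still open on Day 183 and the test is excluded. Nor can the stronger reading stand beside the 6 to 15 of 49 count: if the switch ended with the last wrong dose, all 49 pairs would be kept. Figure 6.3: 1 may settle this, but it was not available for this check.

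A reader might also call the row a contradiction of the plan's stated strategy. It is better described as a pre-specified rule that names both directions and gives a wrong result in one of them. The table is itself the statement of strategy.

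The rest of the opposing case concerns size, and it largely stands. Post-baseline MCCB is scheduled only at Weeks 12 and 26 or at early end of treatment, so most errors would touch no test. Protocol 6.1 returns rescheduled visits to the original calendar, so the equal weighting of day pairs is only illustrative. After a Visit 9 error corrected on Day 169, a Day 183 test is already outside REP. The 2-point effect was seen after 12 weeks of treatment, so a few days or weeks of exposure would probably give less.

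**Conclusion.** The rule is wrong as written for placebo to iclepertin, and the matter is minor. Values from about the first 12 days on active drug, and from the residual period afterwards, stay in the placebo arm as valid hypothetical data. Counting REP from the last correct dose, a switch of 12 days or less excludes nothing.

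The Week 26 analysis can be reached through a short Visit 10 to EoT gap, a Visit 9 error followed by a Day 180 test, or an early-termination test. Whether a nominal Day 183 test after a Visit 10 error is kept cannot be decided from the text, because the end of a switch is undefined.

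The upper bound of 0.009 points per affected patient assumes the full 2-point effect and 220 evaluable placebo patients. How often such errors occur is not stated. If the drug works, the bias is toward no difference. If it does not, contamination changes nothing, so a reader should not infer a threat to the type I error rate.

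**What to change.** Split the row in SAP Table 6.3: 1 by direction.

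- Iclepertin to placebo: keep the current rule.
- Placebo to iclepertin: exclude data from the first iclepertin dose to the last iclepertin dose + REP (12 days). A 21-day switch would then exclude 21 + 12 = 33 days instead of 9.
- Define the end of the treatment switch as a date (last wrong dose or first correct dose), state whether REP is counted from the switch or from the last correct dose, and say how the boundary day and an error at the last dispensing visit are treated. Align Figure 6.3: 1 if needed.

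The cost is one table row, a definition and a line of derivation code. At most a few more values are set to missing and handled by the MMRM. Making the change before unblinding avoids a later decision about which placebo values count.
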